9.0 Data and Safety Monitoring Plan

9.1 Periodic evaluation of data

Data will be entered in REDCap for each participant's visit. Data reported entered into the REDCap data capture forms will be transcribed from source documents

and must be consistent with the source documents or the discrepancies will be explained. Patient Reported Outcomes will be reviewed at each scheduled visit. Safety data will be reviewed on an ongoing basis. Endpoint data will be reviewed periodically and at the end of the study. The Penn State College of Medicine Department of Public Health Sciences Clinical Trial Monitoring unit will oversee study monitoring according to the established Monitoring Plan.

9.2 Data that are reviewed

The PI, Sub-Is, and study team will review and identify adverse events. The sponsor will also review any identified AEs. Study team members will input all data into RedCap and will review input Patient Reported Outcomes. PI and Sub-Is will evaluate eligibility and ensure the integrity of all clinician assessments. Study statisticians may conduct reviews of study data periodically to evaluate the endpoints or perform data quality checks.

The PI will conduct a regular review of the ongoing study with study staff members.

9.3 Method of collection of safety information

Adverse events will be monitored from the time the participant signs the informed consent form up until the end of the study period. Adverse events that begin or worsen after informed consent will be recorded on the Adverse Event Form in the REDCap study forms regardless of the assumption of a causal relationship with the study drug. Conditions that were already present at the time of informed consent should be recorded on the Medical History in the REDCap study forms. Adverse effects and safety information will be collected at study visits with subjects.

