7.2 Study Procedures**7.2.1 Screening visit**

Informed consent	Laboratory screening obtained* 
 • Hepatitis B and Hepatitis C surface and core antibodies • Interferon-releasing assay for tuberculosis (or chest x-ray for those with a history of positive PPD) • Complete blood count (CBC) with differential • Hepatic panel (AST, ALT, Alk phos) • Fasting lipid panel (total, high-density, and low density cholesterol and triglycerides) • Pregnancy testing for women of child bearing potential (WOCBP)**
Inclusion/exclusion criteria reviewed	
Complete physical exam	
Clinician assessments (Lesion count, Hurley stage, HASI)	
Clinical photography of all lesions (do not include face)- kept in research files	
ECG	
Alcohol intake and recreational drug use	
Begin weekly surveys (more details below)	

*All blood will be obtained at Penn State Health outpatient laboratory.

**If subjects are postmenopausal, (defined as amenorrhea at least 12 months before screening) this will be confirmed by FSH levels drawn at the clinical site (approx. 2 teaspoons of blood)

Begin weekly surveys – These will be completed by the participants weekly through the end of Week 16 through REDCap. The weekly instruments will include patient-reported measures: NRS pain with 24-hour recall, NRS pain with 7-day recall, Hidradenitis suppurativa Quality of Life instrument (HiSQOL); medication use (assessing use of rescue medications or other potentially modifying medications or interventions).

7.2.2 Week 0, Baseline visit (28 ±5 days)- Can be combined with Screening Visit

Subjects will have a combined Screening/Baseline visit if all Inclusion/Exclusion criteria is met at the Screening visit.

Complete physical exam	Patient reported measures- collected electronically
------------------------	---

Clinician reported measures collected	WOCBP only- urine sample for pregnancy
Clinical photography	Dispense and start treatment with topical ruxolitinib 1.5% cream. Study coordinator will provide instructions for twice daily application.
Target lesion evaluated	Tissue sample collected (details below)

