7.2.4 Week 8 (± 5 days)

Clinical photography	Target lesion evaluated
Patient reported measures- collected electronically	All used/ unused study medication returned
Clinician reported measures	New study medication dispensed
Complete physical exam	WOCBP only- urine sample for pregnancy

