7.2.5 Week 16/Early Termination (± 5 days)

Clinical photography	Laboratory Testing (approx. 8 tsp blood):
Complete physical exam	
 • CBC with differential • Hepatic panel (AST, ALT, Alk phos) • Fasting lipid panel (Total, high-density, and low density cholesterol, and triglycerides) • WOCBP only- urine sample for pregnancy
Patient reported measures-completed electronically	
Clinician reported measures	
Tissue sample collected (details below)	
Target lesion evaluated	
All dispensed medication (used and unused) will be returned to the research office	

Tissue sample of Target lesion identified at the baseline visit (whether active or resolved): We will collect a full-thickness skin punch biopsy (4-6mm) from the target lesion.

For all full-thickness skin punch biopsies, skin punch will be immediately placed in sterile specimen cup and transported on ice to [name] laboratory (C7801 BMR) for storage and analysis.

Biopsy will be bisected and portions will be formalin-fixed paraffin-embedded for planned immunohistochemistry analyses.

Remaining biopsy portion will be placed in RNALater and stored at -80C. Total RNA will be isolated from the skin punch and may be subjected to RNA-sequencing in future studies.

7.2.6 F/U Telephone Call (30 days post last dose of study medication) (+7 days)

Coordinator will call participant and discuss any new A/E's or changes in medication since the last dose of study medication.

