9.4 Frequency of data collection

Adverse events will be monitored at study visits from the time the participant signs the informed consent form up until the end of the study period. Study visits will occur at Screening, Baseline (Week 0), 4, 8, and 16. If there is a potential clinically significant abnormality in laboratory assessments, then an unscheduled visit the following week will be scheduled to repeat laboratory assessments is required.

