18.2 Recording and Reporting of Adverse Events

Research subjects will be routinely questioned about adverse events at study visits. All adverse events (serious or non-serious) and abnormal test findings observed or reported to study team believed to be associated with the study drug(s) or device(s) will be followed until the event (or its sequelae) or the abnormal test finding resolves or stabilizes at a level acceptable to the investigator. Adverse events will be monitored from the time the participant signs the ICF up until the end of the 24-week study period. Adverse events (including laboratory abnormalities that constitute AEs) will be described using a diagnosis whenever possible rather than by underlying signs and symptoms.

An abnormal test finding will be classified as an adverse event if one or more of the following criteria are met:

- The test finding is accompanied by clinical symptoms
- The test finding necessitates additional diagnostic evaluation(s) or medical/surgical intervention; including significant additional concomitant drug treatment or other therapy
- The test finding leads to a change in study drug dosing or discontinuation of subject participation in the clinical research study
- The test finding is considered an adverse event by the investigator.

SAE Reporting to Incyte

The Principal Investigator (PI) must report all Serious Adverse Events (SAEs) to Incyte within 24 hours of learning of an event, regardless of the PI's causality assessment. This notification should be provided on a completed Serious Adverse Event (SAE) form. SAE reporting for each subject begins the day the informed consent is signed by the patient and within 30 days after subject has completed or discontinued from the study or has taken last dose of the study drug, or as described in the protocol.

SAEs, occurring using Incyte study drug, are reported in accordance with the effective protocol. SAEs occurring with any other commercial drug are reported to the manufacturer of that drug in accordance with regulations and protocol.

Initial SAEs and/or subsequent follow-up reports should be reported via email to [contact] or fax [name]. SAE reports should be for a single subject. SAE forms should be sent with a cover sheet and any additional attachments.

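### During treatment, adverse events are scheduled to be asked about only at visits, so none is asked about for up to 66 days between Week 8 and Week 16, although participants complete a survey every week

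*Combined protocol and SAP*

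**What the plan says.** **AE enquiry.** Section 9.3: "Adverse effects and safety information will be collected at study visits with subjects". Section 18.2: "Research subjects will be routinely questioned about adverse events at study visits". Section 9.4 also ties AE monitoring to visits and gives the schedule: "Study visits will occur at Screening, Baseline (Week 0), 4, 8, and 16". Sections 7.2.4 and 7.2.5 allow ±5 days at Week 8 and at Week 16, and nothing is scheduled between them.

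**Weekly survey.** Section 7.2.1: "These will be completed by the participants weekly through the end of Week 16 through REDCap". The listed content is two pain scales (24-hour and 7-day recall), HiSQOL, and "medication use (assessing use of rescue medications or other potentially modifying medications or interventions". No AE item is listed.

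**Review.** Section 9.1: "Patient Reported Outcomes will be reviewed at each scheduled visit". The same section promises continuing review of safety data, and section 9.2 has the team review patient-reported outcomes. Neither gives an interval.

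**Other routes.**
- Section 7.4.6.5 reconciles medications through the surveys or visits for the whole study.
- Section 18.2 covers events that reach the team by observation or report.
- Section 7.2.6 adds a telephone call 30 days (+7) after the last dose that asks about new AEs.
- Section 9.4 provides an unscheduled visit after a possibly significant laboratory abnormality.

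**The concern.** The longest stretch without a planned enquiry falls in the second half of treatment. Several of the plan's own provisions depend on events becoming known during it:

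- The risk table in section 10.0 handles systemic infection by monitoring throughout the study, naming laboratory tests, vital signs and AE monitoring as examples. Safety blood tests are listed only at Screening and Week 16.
- The table in section 18.2 sets actions on study drug for AEs that could be drug-related, including Grade 1 and 2 events. A participant may not think to volunteer such an event.
- The 24-hour reporting time for serious events starts when the investigator learns of the event.
- Section 9.7 tabulates AE incidence. Events recalled after eight or nine weeks are easier to miss and harder to date.
- Section 18.7 plans no stopping rules, and section 9.6 plans one cumulative review after all data are in. Timely detection therefore rests mainly on individual participants' reports.

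Meanwhile a weekly electronic contact already runs through the whole period and, as listed, does not ask about AEs.

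**Working it through.** The plan states no gap length, so there is no figure to reproduce. The check is calendar arithmetic on the visit windows, counting Baseline as Day 0.

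**Inputs**
- Week 8 (section 7.2.4): Day 56 ± 5, so Days 51 to 61.
- Week 16 (section 7.2.5): Day 112 ± 5, so Days 107 to 117.
- Survey interval (section 7.2.1): 7 days.

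**Week 8 to Week 16**
- Nominal: 112 − 56 = 56 days.
- Shortest: 107 − 61 = 46 days.
- Longest: 117 − 51 = 66 days.
- Nominal share of treatment: 56 / 112 = 50%.
- Surveys falling due: 56 / 7 = 8 nominally; 66 / 7 = 9.4, so 9 in the longest gap.

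**Earlier gaps, for comparison**
- Baseline to Week 4, longest: 28 + 5 = 33 days.
- Week 4 to Week 8, longest: 61 − 23 = 38 days.

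**Whether another provision fills the gap**

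| Provision | Scheduled AE enquiry or dated review between Weeks 8 and 16? |
|---|---|
| Continuing safety review (9.1) | No: no interval given, and it reviews data rather than asking participants |
| Team review of patient-reported outcomes (9.2) | No: no interval given |
| Medication reconciliation (7.4.6.5) | No: covers medications, no interval given |
| Events reported to the team (18.2) | No: depends on the participant coming forward |
| Unscheduled visit (9.4) | Unlikely to arise: it follows a laboratory abnormality, and no safety blood test is listed at Week 4 or Week 8 |
| Telephone call (7.2.6) | No: 30 days after the last dose |

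**With an AE item in the weekly survey**
- Longest interval between scheduled enquiries: about 7 days instead of 66, if surveys are completed.
- Longest time from one enquiry until staff have reviewed the next answer, with weekly review: about 7 + 7 = 14 days.

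**The case against.** A reader might infer that nobody reads the surveys until treatment has ended, that there is no safety contact for 66 days, or that safety detection fails in the second half of treatment. The documents do not support any of these. Section 9.1 says that patient-reported outcomes are reviewed at each visit, not that they are reviewed only then, and it promises continuing safety review. Rescue or modifying treatments are reported weekly and reconciled through the surveys, so they are captured near the time of use; only the speed of any response is open. Participants may report events at any time, and the provision in section 7.4.6.5 for an acutely painful lesion implies contact when needed. The consent form and the separate monitoring plan are not in the material reviewed, and either may describe a reporting route. Nothing in the documents shows that recall shifts onset dates in a particular direction.

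It can also be said that this is a small, single-site, open-label study of a topical product that the protocol regards as having low systemic exposure and as not high risk, so visit-based collection is a defensible choice.

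Finally, asking more often has a consequence under the plan's own rules. Section 18.2 takes a participant off study drug for a possibly related Grade 1 or 2 event, and sections 1.2 and 8.3 limit the primary analysis to completers. Section 8.1 wants at least 18 completers from about 24 people screened and enrolled, a margin of 24 − 18 = 6 that must also cover screen failures and losses.

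All of this stands as a limit on the wording and as a cost to name. It does not supply a scheduled enquiry or a dated review between Week 8 and Week 16.

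**Conclusion.** The point holds in a limited form. During treatment, AE enquiry is scheduled only at visits. This leaves 56 days nominally (46 to 66 within the windows) without a scheduled enquiry, and the nominal figure is half of the treatment period. The weekly survey that spans this interval lists no AE item, and no review of it between visits is dated. Mild or non-serious events may therefore be under-recorded or imprecisely dated. The documents give no basis for estimating how many.

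The day counts assume Baseline as Day 0 and visits held within their windows. The reduction to about 7 days assumes that surveys are completed. The point is a cheap improvement to a workable plan and should not be read as a finding that safety monitoring is absent.

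**What to change.** - **Section 7.2.1:** add one item to the weekly survey asking whether there has been any new or worse health problem since the last survey, with space to describe it.
- **Sections 9.1 and 9.3:** state that a positive answer, or any new medication or intervention entry, is flagged to the coordinator and reviewed at least weekly. State that any AE found this way is recorded with its onset date. This would also define how continuing safety review works between visits.
- **Section 9.7 (optional):** mark each AE as elicited by survey or at a visit, so that the effect of asking more often on incidence can be seen.

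**Cost.** One survey item, one flag and a little coordinator time. No visit or procedure is added, and section 3.2 already excludes people without reliable internet access for the surveys. More mild AEs will probably be reported. The sponsor should note in the plan that, with the section 18.2 table as written and a completers-only primary analysis, this could affect the number of completers.

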9.4 Frequency of data collection

Adverse events will be monitored at study visits from the time the participant signs the informed consent form up until the end of the study period. Study visits will occur at Screening, Baseline (Week 0), 4, 8, and 16. If there is a potential clinically significant abnormality in laboratory assessments, then an unscheduled visit the following week will be scheduled to repeat laboratory assessments is required.

9.5 Individuals reviewing the data

Data will be reviewed first by study team members for safety and integrity, and then by staff from the Penn State College of Medicine Department of Public Health Sciences Clinical Trial Monitoring unit.

9.6 Frequency of review of cumulative data

Cumulative data will be reviewed once after data is collected on all participants.

9.7 Statistical tests

A treatment-emergent adverse event is any adverse event (AE) either reported for the first time or worsening of a pre-existing event after first use of the study drug.

Analysis of AEs will be limited to treatment-emergent AEs, but data listings will include all AEs regardless of their timing to study drug administration. Adverse events will be coded using MedDRA and tabulated by preferred term and system organ class. Severity of AEs will be based on the CTCAE v4.03 using Grades 1 through 5. The subset of AEs considered by the investigator to have a relationship to study drug will be considered to be treatment-related AEs. If the investigator does not specify the relationship of the AE to study drug, then the AE will be considered treatment-related. The incidence of AEs and treatment-related AEs will be tabulated.

Actual values and changes from baseline in clinical laboratory test results will be summarized using descriptive statistics. Laboratory test values outside the normal range will be assessed for severity based on the normal ranges for the clinical reference laboratory. The incidence of abnormal laboratory values will be tabulated. Laboratory data will be classified into Grades 1 through 4 using CTCAE v4.03. The number and percentage of participants with worst post-baseline CTCAE grade (regardless of baseline value) will be summarized. Each participant will be counted only for the worst grade observed post-baseline. Shift tables from baseline to the worst post-baseline value using CTCAE grade. For laboratory parameters where CTCAE grades are not defined, shift tables to the worst post-baseline value using the low/normal/high classifications based on laboratory reference ranges will be provided.

9.8 Suspension of research

The research will be suspended if it is found by the IRB that it is not being conducted in accordance with regulations or IRB requirements, or that has been associated with unexpected serious harm to human subjects, or where suspension or termination has been initiated by a sponsor or other outside entity.

10.0 Risks

Potential Risk of Clinical Significance	Summary of Data Available/ Rationale for Risk	Mitigation Strategy
Universal risks to participation in an HS clinical trial		
Aggravation of HS	Worsening of HS may occur either as a spontaneous event or due to insufficient efficacy of the study medication.	Participants can receive up to 2 lesional rescue interventions or, in the event of superinfection, a short course of antibiotic treatment Participants may also withdraw from the study at any time for any reason (see Section Error! Reference source not found.), in which case, they would be able to use alternative conventional treatments for their HS.
Loss of Confidentiality	Identifiable or private information about the subject becomes lost or known to others	Study data will be stored in locked offices, password protected files, and encrypted when appropriate for the type of data. Only the study staff and Clinical trial monitoring staff will be given access.

Risks associated with topical administration of ruxolitinib		
There have been no serious adverse reactions for ruxolitinib cream.		
Drug reactions	With low systemic exposure for topical application of ruxolitinib cream, it is unlikely that meaningful levels of plasma metabolites, active or otherwise will be present.	No precautions needed for concomitant use with other medications.
Prenatal and postnatal exposure	There is inadequate data related to the effect of topical ruxolitinib in a developing fetus or whether it passes into breastmilk.	Pregnant or breastfeeding women will not be included in the trial. Women will be asked to use a contraceptive method.
Photo-induced skin reaction	There is a theoretical risk of a skin reaction with topical ruxolitinib use and ultraviolet light (UV) exposure.	Participants will be counselled to avoid UV light exposure or use a standard method of protection such as sunscreen or UV-protective clothing.
Risks associated with systemic administration of ruxolitinib		
No clinically meaningful systemic adverse events have been found to be associated with the use of ruxolitinib cream in its clinical studies performed to date in alopecia areata, psoriasis, atopic dermatitis, and vitiligo.		
Risk of systemic infections	Longer-term oral treatment with ruxolitinib can cause immunosuppression, allowing secondary infections.	Participants will be tested at the study entry for latent TB infection, chronic hepatitis,, and monitored for any signs and symptoms of infection throughout the study (eg, clinical laboratory tests, vital signs, and AE monitoring). In the event of an infection necessitating such steps, study medication can be withheld or stopped and appropriate anti-infective therapy instituted.
Headaches	Mild to moderate headaches were observed in a proportion of healthy volunteers exposed to ruxolitinib.	Possible headaches will be captured by routine AE monitoring. Analgesics may be used to relieve headache, if appropriate.

11.0 Potential Benefits to Subjects and Others

11.1 Potential Benefits to Subjects

Participants may experience clinically meaningful improvements in their HS lesions during the study and may additionally benefit from the comprehensive safety assessments conducted as part of the study (eg, clinical laboratory tests, physical examinations). They may also feel a psychological benefit from contributing to the process of studying a therapy for HS, a disease with high unmet need that is severely debilitating to participants' well-being and daily functioning.

11.2 Potential Benefits to Others

This may also contribute to the process of developing a novel anti-inflammatory agent for HS, a disease with high unmet need that is severely debilitating to participants' well-being and daily functioning.

12.0 Sharing Results with Subjects

Sharing individual's laboratory study results is not planned. If a subject requests results then a paper copy will be given directly to the subject at the time of the study visit. If the investigator feels it is important to share a result with a subject's primary care provider, then the result will be faxed, using a cover sheet, to the provider's office fax machine.

Results from research laboratory studies will not be shared with subjects.

13.0 Subject Payment and/or Travel Reimbursements

Subjects will receive \$50.00 per study visit for their participation in this research study for up to a total of \$250.00 . If they do not complete the study for any reason, they will be paid for the visits that were completed. The payment will be provided by Greenphire clincard.

